# 5.1.4 Medical and Surgical History

Medical and Surgical history was collected at Screening. All medical/surgical history data and ongoing medical history will be listed and summarized at Part A + B Baseline for the Safety and PP Analysis Sets by the Medical Dictionary for Regulatory Activities (MedDRA) version 23.0 System Organ Class (SOC) and Preferred Term (PT) and by cohort (wAIHA / CAD).

#### 5.1.5 Prior and Concomitant Medications

#### 5.1.5.1 **Prior and Concomitant Derivations**

Prior and concomitant medications will be coded to the therapeutic drug classes and generic drug names using the World Health Organization (WHO) Drug Dictionary (WHODrug) classifications version March 2021.

Prior medications will include any medications reported with a start date prior to the subject taking their first study dose of Part A Core Study and will be summarized by WHODrug Anatomical Therapeutic Chemical (ATC) Class 3 Term and WHODrug Preferred Name.

Concomitant medications (CM) will include any medications being taken after the subject starts their study medication and will also be summarized by WHODrug ATC Class 3 Term and WHODrug Preferred Name. Hence, medications ongoing at the start of dosing will be counted in both the prior and concomitant medication summaries. Further categorization for concomitant medications will be included in the analysis:

- Part A + B CM: Any medication taken during Part A or Part B of the study. This can include prior medications that were continued into Part A and Part B of the study
- Part B CM: Any medication taken during Part B of the study. This can include prior medications that were taken continuously into Part B of the study. Concomitant medications taken in Part A but ended prior to Part B will not be considered as concomitant medications during Part B.

For the purposes of determining prior/concomitant medications and study part, if a partial date is recorded, the following convention will be used to assign the medication dates:

• If a start date is missing the day information and month/year is the same as first dose date then use first dose date, else '01' will be used

for the day; if a start date is missing the month and the year is the same as first dose date then use first dose date, else January will be used for the start month.

• If a stop date is missing the day information and month/year is same as last study date then use last study date, else last day of the given month will be used for the stop day; if a stop date is missing the month and year is the same as last study date then use last study date, else December will be used for the stop month.

### 5.1.5.2 *Medication Listings*

All prior medications and concomitant medications, interventions and procedures will be presented in listings for all subjects in Safety Set.

The categorization of concomitant medications (CM Part A + B / CM Part B) will be included in the listings.

#### 5.1.5.3 Medication Summary Tables

The following summaries will be tabulated:

- Prior Medications, subjects who had medications prior to entering Part A Core Study Phase in the Safety Set:
  - Frequency of subjects taking prior medications by WHODrug ATC Class 3 and Preferred Name, and by cohort
- Concomitant Medications:

### • **Part** A + B:

- For concomitant medications taken during Part A or Part B: Frequency of subjects by concomitant medication WHODrug ATC Class 3, Preferred Name, and by cohort
- Part B:
  - Frequency of subjects by concomitant medication WHODrug ATC Class 3, Preferred Name, and by cohort

#### 5.1.6 Exposure

All study drug exposure data will be listed based on the Study Drug Administration eCRF.

#### 5.1.6.1 *Compliance Derivations*

The compliance for Part A + B must incorporate the different dosing regimens of the daily APL-2 dosing regimen (Part A) and the twice/three times weekly APL-2 dosing regimen (Part B).

### Part A Compliance

For Part A, compliance will be calculated as:

 $Part A Compliance = \frac{number of complete study doses}{total expected study doses during Part A} x 100$ 

Unless otherwise noted, during the Part A Core Study Phase, the number of expected doses is the number of days during Part A for subjects that did not roll over into Part B. For subjects that rolled over into Part B, the expected number of doses is the number of days during Part A - 1 to account for the skipped dose prior to the dose transition

### Part B Compliance

For the Part B, compliance will be calculated as:

Part B Compliance =

 $\frac{number \ of \ complete \ study \ doses \ administered}{during \ Part \ B \ prior \ to \ study \ discontinuation/completion}{total \ number \ of \ expected \ study \ doses \ during \ Part \ B} x \ 100$ 

That is, when subjects receive twice weekly dosage, percentage compliance will be calculated as:

Part B Compliance =

 $\frac{actual number of complete study doses administered}{(last dose date - first dose date + 3.5)/7) \ge x \ 100$ 

Apellis Pharmaceuticals, Inc.
Protocol: APL2-CP-AIHA-208
Part B Long Term Extension Statistical Analysis Plan

Version 1.0

When subjects receive every 3 days dosage, percentage compliance will

be calculated as:

Part B Compliance =

$$\frac{actual number of complete study doses administered}{\frac{last dose date - first dose date}{3} + 1} x \ 100$$

### Part A + B Compliance

Using the above, the compliance during Part A + B period will be calculated as:

Part A + B Compliance =

number of complete study doses administered + number of complete study doses administered during Part A + during Part B + 100

 $\frac{100}{100}$  total number of expected study doses during Part A + total number of expected study doses druing Part B x 100

5.1.6.2 *Exposure and Compliance Listings* 

All APL-2 Study Drug administration and Drug accountability will be listed. Compliance during Part A + B and Part B will be listed by subject.

### 5.1.6.3 Exposure and Compliance Summary Tables

The following exposure and compliance parameters will be summarized by Part A + B and Part B and cohort (Cohort 1 wAIHA / Cohort 2 CAD):

- Total dose administered summary statistics
- Duration (total dosing period in days) summary statistics
- Compliance summary statistics
- Compliance frequency categories (Compliance < 80% / 80% ≤ Compliance < 90% / 90% ≤ Compliance < 100% / 100% ≤ Compliance < 120%

### 5.2 Safety Analysis

The primary objective of the study is to assess the safety and tolerability of APL-2. The safety analyses will be performed on Safety Set per the specifications outlined in the subsections below.

#### Version 1.0

#### 5.2.1 Adverse Events

#### 5.2.1.1 Treatment-Emergent Adverse Events (TEAE)

TEAEs are defined as those AEs that occur after Dosing on Day 1, or worsen in severity, and up to 8 weeks (56 days) after the last dose of APL-2.

AEs will be considered Treatment-Emergent (TEAE) unless there is clear indication that the event occurred prior to first dose of study drug. AEs present prior to the first dose of study drug administration that increased in severity or relationship to study drug after the first dose of study drug and up to 56 days beyond the last dose of study drug will be classed as a TEAE. Events with missing or partial dates will be handled such that in the absence of contradictory information an AE is Treatment-Emergent. So, for a missing start date (where stop date is after date of first dose) the date will be imputed as the date of first dose; for a missing stop date the date will be imputed as the last study date. If a partial date is recorded, the following convention will be used to assign the AE:

- If a start date is missing the day information and month/year is the same as first dose date then use first dose date, else '01' will be used for the day; if a start date is missing the month and the year is the same as first dose date then use first dose date, else January will be used for the start month.
- If a stop date is missing the day information and month/year is same as last study date then use last study date, else last day of the given month will be used for the stop day; if a stop date is missing the month and year is the same as last study date then use last study date, else December will be used for the stop month.

#### 5.2.1.2 Treatment-Emergent Adverse Event Study Part

TEAE will be summarized by study part in Safety Set using the following definitions:

• Part A + B: will include all TEAE from a start date on or after the first dose of APL-2 in Part A up to 8 weeks (56 days) after the last

dose of APL-2 in Part B.

• Part B: will include all TEAE during Part B which is any AE with a start date on or after the date of first 1080 mg APL-2 dose up to the end of 8 weeks (56 days) after the last dose of APL-2 in Part B.

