## Adverse Events Summary

An AE data listing of all AEs collected on study, including verbatim term, preferred term, treatment, severity, and relationship to treatment will be provided. Serious Adverse Events (SAEs), adverse events of special interest, and details of subjects withdrawing due to adverse events will also be listed. The start day (relative to the first dosing day), and the duration of AEs will be included in listings.

A topline summary for Part A, Part B, and Overall will present the number of events and the number of subjects by randomized dose level and by cohort with:

- any TEAE
- any TEAE considered as related to study drug (evaluated by the investigator as Unlikely Related, Unrelated, Possibly Related, Probably Related, Definitely Related, or Unknown)
- any serious TEAE
- Maximum severity TEAE of mild, moderate, severe, life threatening, and death; i.e. a subject with TEAEs at different intensities will be summarized at the most severe intensity
- any TEAE of special interest
- any TEAE leading to study drug discontinuation
- any TEAE leading to death

The table will also include the total number of TEAEs reported in each cohort and overall. The total number of unique terms within subjects will also be presented, counting each TEAE only once within each subject.

Additionally, the following will be tabulated with the number of events and the number/percent of subjects by randomized dose level in each cohort, and by cohort. Summaries will be ordered by descending order of event count in the overall column. All summary tables will be presented by study part and over the whole study, where AEs will be categorized by the Part in which the AE started i.e. an AE which began during the Part A Core Study Phase will be categorized under Part A even if it continues into Part B (unless it increases in severity).

- TEAEs by SOC and preferred term
- TEAEs by preferred term

• TEAEs regarded as at least possibly related to study drug by SOC and preferred term

The following will also be tabulated with the number/percent of subjects by randomized dose level in each cohort and by cohort:

- TEAEs and Serious AEs by SOC, preferred term, and maximum severity
- TE AESIs by SOC, preferred term, and maximum severity if applicable
- TE AESIs (regarded as at least possibly related to study drug) by SOC, preferred term, and maximum severity

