#### 3.2 Study Endpoints

#### 3.2.1 Primary Safety Endpoint

The primary safety endpoints of the study are the incidence and severity of Treatment-Emergent adverse events (TEAEs) following administration of multiple doses of SC APL-2.

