#### 3.3 Study Design

This is a Phase II, open-label, prospective pilot study of APL-2 conducted in subjects with a primary diagnosis of wAIHA or CAD in parallel. The study will consist of up to 24 subjects, a target of 12 subjects with a primary diagnosis of wAIHA in Cohort 1 and a target of 12 subjects with a primary diagnosis of CAD in Cohort 2. Subjects will be randomized 1:1 to a 270mg or 360mg daily SC APL-2 dosage group within each cohort for up to 12 months (Part A, the Core Study Phase).

Following Day 336 and the completion of the Part A Core Study Phase, subjects will be eligible to participate in Part B, a Long-Term Extension Phase, in order to continue to receive treatment with APL-2. The Long-Term Extension Phase is described later in this section.

Through Part A (Day 336), dose escalation from 270 mg/d to 360 mg/d, or deescalation from 360 mg/day to 270 mg/day may occur after a thorough evaluation of available safety and laboratory assessment.

Safety will be assessed throughout the study; serial blood and urine samples will be collected for these assessments. Blood samples will be collected for the assessment of APL-2 PK. Additional samples for assessment of PD will also be collected.

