#### 3.3.1 Sample Size Considerations

As this is a pilot study the sample size is not based on formal statistical testing. The sample size is considered sufficient to obtain useful safety, tolerability, PD, and PK data to assist the planning of future studies.

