### 4.3 Test Hypothesis and P-Value Justification

No formal inferential statistics will be applied to data collected in this study.

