#### Part B:

Part B EAI will be determined for Part B TEAE (i.e. AE with a start date on or after the date of first 1080 mg APL-2 dose). It is defined as the number of events divided by the total duration of exposure of the subjects at risk during Part B treatment, which is computed as following:

Part B Exposure Adjusted incidence rate (e) =  $n*100/EY_B$ 

where:

- *n* is the number of subjects with an event
- *Exposure year* (*EYB*) = (sum of time to onset of the event)/365.25
- Time to onset of the event = date of onset of event date of the first 1080 APL-2 dose +1

For subjects without the event, time to onset is censored as follows: *Time to onset of the event = last dose date + 56 days – first 1080 mg APL-2 dose date +1* 

For subjects who experienced the same event on multiple occasions: Time to onset of the event = date of onset at the first occasion - first 1080 mg APL-2 dose date +1

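### The Part B SAP assigns adverse events to Part B by start date alone, so an event that began in Part A and worsened on 1080 mg can drop out of the Part B TEAE tables

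*SAP*

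**What the plan says.** The primary endpoint covers both frequency and grade: "The primary safety endpoints of the study are the incidence and severity of Treatment-Emergent adverse events (TEAEs" (Part B SAP 3.2.1). The general definition in 5.2.1.1 has two limbs, onset and worsening: "TEAEs are defined as those AEs that occur after Dosing on Day 1, or worsen in severity". The sentence that elaborates the second limb concerns events already present before the first dose of study drug, which is Part A Day 1.

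Section 5.2.1.2 then allocates events to study parts. Part B takes "any AE with a start date on or after the date of first 1080 mg APL-2 dose", up to 56 days after the last dose. Section 5.2.1.4 restates this for the Part B exposure-adjusted rate: "i.e. AE with a start date on or after the date of first 1080 mg APL-2 dose". Neither place mentions worsening.

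The SAP of 27 April 2020 (Adverse Events Summary, under 5.2.1) had a different rule at the switch. An event that began in Part A "will be categorized under Part A even if it continues into Part B (unless it increases in severity"). The Part B SAP of 8 November 2022 does not repeat that exception and does not comment on leaving it out.

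**The concern.** The Part B column is where the 1080 mg regimen is described separately from the daily regimen. Section 5.2.1.6 reports by cohort and study part: any TEAE, serious TEAEs, maximum severity, discontinuation and death, then SOC/PT tables and severity tables. All the Part B entries use the 5.2.1.2 allocation.

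If an event starts on daily dosing, is mild at the switch and becomes severe on 1080 mg under the same record, its start date keeps it out of Part B. The change in severity, which is part of the primary endpoint, is then not shown against the regimen on which it happened. Where the rule has an effect on worsened events, it can only lower the Part B figures. Because the SAP states "No formal inferential statistics will be applied to data collected in this study", these descriptive tables are the result, and no later model would recover the information.

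**Working it through.** The plan has no figure to reproduce: "the sample size is not based on formal statistical testing", and no event rate is assumed. The check applies the two allocation rules to one example and then works out what one omitted subject is worth.

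**Rules applied to one event.** The example days are assumed: onset on Day 300, first 1080 mg dose on Day 336, worsening on Day 400, last dose on Day 1066.

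- Part B SAP rule: counted in Part B if 336 ≤ start ≤ 1066 + 56. Start = 300, so it is **not counted**.
- General worsening clause (5.2.1.1): needs an event present before the first dose of study drug (Day 1). Onset on Day 300 is later, so the clause **does not apply**.
- 2020 SAP rule: by part of onset, except where severity increases. Worsening on Day 400 falls after the switch, so it is **counted in Part B**.
- The same event ending treatment with no rise in severity: **neither** rule places it in Part B.

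**Effect on a percentage row.** One subject is 100/n. The SAP gives "a target of 12 subjects with a primary diagnosis of wAIHA in Cohort 1", and likewise 12 for CAD, so 12 is the planned upper bound. The number who rolled over is not stated, so smaller n are assumptions.

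- n = 12: 100/12 = 8.3 points
- n = 8: 100/8 = 12.5 points
- n = 6: 100/6 = 16.7 points

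The row moves only if that subject has no other Part B event qualifying for it. For the severe row that means no other severe Part B TEAE. For the any-TEAE row it means no other Part B TEAE at all.

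**Effect on the exposure-adjusted rate.** The formula in 5.2.1.4 is rate = (subjects with event) × 100 / EY, where EY is the sum of times to onset divided by 365.25. A subject without the event contributes last dose + 56 − first 1080 mg dose + 1 days. For a subject dosed through Part B Day D this is D + 56. Worsening on Day 400 is Part B Day 400 − 336 + 1 = 65. Assume every subject has the same D, and that this is the only subject with the event.

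- n = 12, D = 365. As written: EY = 12 × 421/365.25 = 13.83, rate 0. With worsening counted: EY = (11 × 421 + 65)/365.25 = 12.86, rate 100/12.86 = 7.8 per 100 exposure-years.
- n = 12, D = 1176 (the last target day in the windowing table). As written: EY = 12 × 1232/365.25 = 40.48, rate 0. With worsening counted: EY = (11 × 1232 + 65)/365.25 = 37.28, rate 2.7.
- n = 8: the rate goes from 0 to 12.1 (D = 365) or 4.2 (D = 1176).

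As written, the subject is missing from the numerator and also adds full follow-up to the denominator.

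**The case against.** The main objection is that the loss depends on how sites record worsening. Protocol 14.1 counts exacerbation of a pre-existing condition as an AE, and requires a condition present at screening to be recorded as an AE if its severity changes. If sites do the same for on-study events, the worsening has its own start date and 5.2.1.2 already counts it. The documents do not say what happens for on-study events, and the eCRF completion rules are not among them. This stands: the undercount is conditional.

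The events are also not hidden. They remain in the Part A + B columns and in the AE listings, which give a study day relative to Part B baseline. The disposition table gives reasons for withdrawal in Part B whatever the AE onset date. With at most 12 planned per cohort, the listings can be read subject by subject. This also stands, although the Part A + B column pools the regimens and the listing is not said to date the worsening.

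A reader might go further and infer that pre-existing types of event, such as infections, injection-site reactions or haemolysis, are removed from Part B as a class, or are the ones most likely to worsen. The documents support neither. A new episode on 1080 mg has a new start date and counts, and nothing in the plan ranks events by likelihood of worsening.

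A reader might also infer that the discontinuation and death rows are wrong unless reassigned by date of outcome. The 2020 exception covered only increased severity, and allocation by onset is a common convention, so reassigning those rows would be a preference.

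Finally, the 2020 SAP served the interim Part A analysis and does not govern the final one. The difference is an unexplained change between plans, not a contradiction within the governing plan.

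**Conclusion.** The gap is real but limited. On its text, the Part B SAP has no route by which an event that began in Part A and worsened on 1080 mg under one record enters the Part B incidence, maximum-severity or exposure-adjusted tables. For such events the undercount runs in one direction.

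Each affected subject is worth 8.3 percentage points at n = 12 and 16.7 at an assumed n = 6, given no other qualifying Part B event. Under the assumptions above, the exposure-adjusted rate moves from 0 to between 2.7 and 7.8 per 100 exposure-years at n = 12. These are sizes per subject, not estimates of total bias. The number of such subjects is unknown and may be zero, and there is no loss if worsening opens a new record.

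This is a should-fix. The study is a descriptive pilot, the events are retained elsewhere, and Part B withdrawals are tabulated by reason. The documents do not support calling the Part B safety result invalid, or saying that worsening on 1080 mg goes wholly unreported.

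**What to change.** In 5.2.1.2 and 5.2.1.4, define a Part B TEAE as an AE that starts, or increases in severity, on or after the first 1080 mg dose and up to 56 days after the last dose. For an event that qualifies by worsening, use the worsening date as its Part B onset, including in the time-to-onset calculation.

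State how worsening of an on-study AE is recorded. If a new record is always opened, say so, and ensure that the worsening is counted once. If severity changes are not dated, have the AEs ongoing at each subject's switch medically reviewed before database lock. With cohorts of this size the list should be short.

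Optionally, footnote the Part B discontinuation and death rows with any such outcomes in Part B that arose from AEs with earlier onset, so that they can be reconciled with the Part B withdrawal reasons in the disposition table.

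The cost is one clause in two sections, one derivation and possibly one short review. No design change or new data collection is needed.

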### 5.2.1.3 Adverse Events of Special Interest and Special Search Categories

Version 23.0 of MedDRA will be used to classify all AEs. Per Protocol Version 1 Amendment 4, Protocol Adverse Events of Special Interest (AESI) include the following categories and Standardized MedDRA Queries (SMQ):

- Local or systemic infection of any origin (AE SOC = "Infections and Infestations")
- Clinically significant decrease in kidney function, defined as AE SOC = "Renal and Urinary Disorders" or AE SOC = "Investigations" with AE PT = "Blood Creatinine Increased Creatinine"
- Injection site reactions (as collected in eCRF)
- Thrombotic events (Thrombophlebitis SMQ = 20000081 or AEHLGTCD = 10014523, Embolic and Thrombotic Events SMQ = 20000115)

Additionally, the following TEAE Special Search Categories will include the following:

- Haemolytic Disorders (SMQ = 20000019)
- Hypersensitivity (SMQ = 20000214)
- Sepsis (SMQ =20000234)
- Infections (any AE under AESOC = "Infections and Infestations")
- Thrombosis (Thrombophlebitis SMQ = 20000081 or AEHLGTCD = 10014523, Embolic and Thrombotic Events SMQ = 20000115)

AESIs will be determined by a review of all AEs by the clinical and data management study staff. This review will allow for the inclusion of AEs of special interest arising during the study that are not on the above list, based on a clinical decision. It is expected that documentation of the AEs of special interest will be maintained outside the Medrio database system by the biostatistics and data management staff (with review by medical) and used by the programmer for analysis of the AEs of special interest.

Version 1.0

